### 12.3.2 Overdose Management: not applicable

## 12.4 Annual Safety Report

A yearly safety report will be submitted to the ethical committee up to 1 year following recruitment of the final study patient

## **13 Data Collection and Management**

### 13.1 Monitoring

#### 13.1.1 Composition of data monitoring committee

Given the low number of included patients, the low risk of serious adverse events, and the single-center set-up, no external data monitoring committee is foreseen.

During patient recruitment and up to 3 months following the inclusion of the last study patient, the principal investigator and the co-investigators will review and confirm all data on a 3-monthly basis during a teleconference. All data (outcome, duration of hospital stay, complications) will be gathered on red-cap. No statistical analyses will be performed.

#### 13.1.2 Interim analysis

After the inclusion of the first 5 patients, an interim analysis will be performed to confirm whether the size of the blood sample is adequate, how much bone marrow is extracted and whether this is adequate to do the lab analysis.

### 13.2 Data Collection

Redcap will be used to collect clinical data and translational data.

### 13.3 Database Management and Quality Control

Database management and quality control will be performed by the principal investigator and co-investigators. All study-related documents will be collected and kept in a closed location.

## 13.4 Statistical Considerations and Data Analysis

No statistical analysis will be done in this feasibility trial

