To study the BMN and autologous tumor-bone marrow interactions, we want to collect **blood, bone marrow and lung tissue of 10 lung cancer patients**.

1) This pilot trial is designed to **evaluate the feasibility and safety of obtaining bone marrow upon costal aspiration** during surgery. The rationale for using rib bone marrow aspiration is the easily accessible localization due to trocar placement (in minimally invasive surgery) or during thoracotomy. Previous trials demonstrated the feasibility of micro-metastasis detection in rib marrow aspiration. This procedure was safe without any documented adverse events for patients. We hypothesize that we can use this technique to obtain sufficient bone marrow-derived HSPCs (which represent only 0,1% of the total bone marrow fraction) for *ex vivo* single-cell evaluation, optimization of a 3D BMN platform^15 and preclinical *ex/in vivo* assessment in patient-derived organoids and murine xenograft models. The use of rib marrow eliminates the need for extra incision as incisions used for trocar placement or thoracotomy will be used. We

hypothesize that the patient will not experience extra discomfort from this technique since every patient undergoing thoracic surgery is treated according to the ERAS protocols with a major emphasis on pain control.

2) If the feasibility and safety of bone marrow aspiration are confirmed by this pilot trial, we plan to conduct a large-scale study in which we will collect and bank blood, bone marrow and tumor per NSCLC patient. With this unique autologous biological material collection, we aspire to conduct innovative research into the current resistance mechanisms of NSCLC to immunotherapy via at least two ongoing research projects:

- a) **X-talk project** with the hypothesis: 'The bone marrow niche of NSCLC patients withholds invaluable information about tumor-installed resistance mechanisms to immunotherapy. By deciphering this information, we aspire to serve the diagnostic and therapeutic field.'
- b) **RADar project** with the aim to answer the following research questions: 1) can we efficiently deliver RADars specifically to human lung tumor cells? and 2) will RADar delivery result in tumor cells' sensitivity to and killing by patient-specific human T cells? To be able to answer these questions in a relevant way, we opt for two meticulous human(ized) immunological models namely:

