### 6.4 Endpoints

1. Safety: the occurrence of complications
2. Feasibility: Obtain a minimum of  $2 \times 10^6$  Lin- CD34+ HSPCs to allow single cell sequencing ( $10^6$ ), bone marrow cultivation ( $5 \times 10^5$  cells per culture) and transplantation in immunodeficient mice ( $10^5$  cells per injection).

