## **7 Investigational Plan**

### 7.1 Overall Study Design

- 1) This trial is a phase I feasibility trial. It is designed to evaluate the feasibility and safety of obtaining bone marrow upon costal aspiration during surgery.
- 2) If feasibility and safety of rib bone marrow aspiration are confirmed in this pilot trial, a large-scale study will be started to optimize and conduct fundamental and translational research via the X-talk project and RADar project (see details under 5.4, page 9).

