#### 7.2.5 *End of Study*

The study will end once 10 study patients have been included. We foresee that the end will be scheduled for 31st of December 2025.

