### 10.3 Known Undesirable Effects of costal rib aspiration

- Pain
- Bleeding
- Infection

In a survey of members of the British Society of Haematology reported in 2003, there were 26 adverse events, including one fatality, out of an estimated total of 55,000 bone marrow biopsy procedures (0.05 percent). A follow-up survey of this group, reported in 2006 involving 20,323 procedures, resulted in the reporting of 15 adverse events (0.07 percent). Previous research evaluating the feasibility to detect disseminated tumor cells in bone marrow aspirate from the ribs couldn't identify any adverse events related to the bone marrow aspiration.

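### The larger study depends on safety and feasibility being confirmed in 10 patients, but no analysis is planned, no confirming result is defined, and 0/10 complications excludes only rates above about 31%

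*Protocol*

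**What the plan says.** Safety and feasibility together form the primary objective (section 6.2). The safety endpoint in section 6.4 is "Safety: the occurrence of complications", with no acceptable rate. The feasibility endpoint is a yield of at least 2×10^6 Lin- CD34+ HSPCs, with no statement of how many patients must reach it.

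Section 7.1 attaches a decision to the result: "If feasibility and safety of rib bone marrow aspiration are confirmed in this pilot trial, a large-scale study will be started". Section 5.4 says the same: "If the feasibility and safety of bone marrow aspiration are confirmed by this pilot trial, we plan to conduct a large-scale study".

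The size is fixed in section 7.2.5, "The study will end once 10 study patients have been included", and no derivation is given. On analysis, section 13.4 says "No statistical analysis will be done in this feasibility trial", section 13.1.1 says "No statistical analyses will be performed", and the synopsis entry for statistical considerations is None.

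The only numeric safety criterion is the early-termination rule, which concerns two grade 3 (or higher) occurrences and is worded differently in sections 7.2.4, 11.1.7, 12.1.4 and 12.2.2. The interim look in section 13.1.2 covers sample adequacy only.

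**The concern.** A decision to expose more patients is tied to a conclusion, and the protocol supplies neither a criterion for that conclusion nor any measure of its uncertainty. A report of no complications in ten patients could be read as meeting the condition in sections 5.4 and 7.1, although such a result is quite likely even when the procedure causes complications fairly often. Feasibility has the same gap: nobody can say in advance whether 6, 8 or 10 patients reaching the cell target would satisfy the condition.

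This is not a detail left to a statistical analysis plan. The protocol rules out analysis in three places, so a plan that reported an interval would contradict it.

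**Working it through.** **Inputs.** n = 10 (synopsis, section 7.2.5). Survey rates from section 10.3. The 95% confidence level is assumed.

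**The plan's own figures.** 26/55,000 = 0.047%, given as 0.05%; 15/20,323 = 0.074%, given as 0.07%. Both reproduce. The sample size of 10 cannot be reproduced, because no precision, acceptable rate or power is stated.

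**Upper limit after 0 of 10.**
- Exact (Clopper-Pearson), two-sided 95%: 1 − 0.025^(1/10) = 0.3085, or 30.8%.
- Exact, one-sided 95%: 1 − 0.05^(1/10) = 0.2589, or 25.9%.
- Rule of three: 3/10 = 30%.
- Wilson, two-sided 95%: z²/(n + z²) = 3.84/13.84 = 27.8%.

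The choice of method moves the limit between about 26% and 31% and does not change the conclusion. After 1 of 10 the exact two-sided 95% interval is 0.3% to 44.5%.

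**How often ten patients show little or nothing.** For an event with true per-patient probability p, P(0) = (1 − p)^10 and P(≤1) = (1 − p)^10 + 10p(1 − p)^9.

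| True p | P(0 of 10) | P(at most 1 of 10) |
|---|---|---|
| 1% | 0.904 | 0.996 |
| 5% | 0.599 | 0.914 |
| 10% | 0.349 | 0.736 |
| 20% | 0.107 | 0.376 |

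The table must be read for one event type at a time. If p is the rate of any complication, the P(0) column shows how easily a clean result arises. If p is the rate of grade 3 or higher events that count towards termination, and patients are counted, the last column is the chance of completing ten patients without reaching two.

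**Feasibility.** Exact two-sided 95% intervals: 8/10 gives 44.4% to 97.5%; 10/10 gives 69.2% to 100%.

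**Denominator.** Section 7.2.5 counts included patients, and section 9.1 includes them at consent, before surgery. Aspiration follows the operation (section 10.1), so fewer than 10 may be aspirated. After no events the two-sided limit would be 1 − 0.025^(1/9) = 33.6% with nine aspirated and 1 − 0.025^(1/8) = 36.9% with eight.

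**The case against.** **A descriptive pilot is a legitimate design.** The stated aim is to evaluate safety and feasibility, and the trial is called a pilot and a feasibility trial throughout. Anyone given x/10 can compute the interval later. This stands, and it limits the severity. It does not remove the gap, because the protocol itself makes a further study depend on the result.

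**A reader might infer that the protocol claims ten patients establish safety.** It does not. The word confirmed, applied to safety and feasibility, appears only in a conditional clause about a later study, and no section says that any complication rate will be excluded. The fault is a condition without a criterion, combined with wording that is too strong.

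**A reader might infer that at most 1 of 10 is the implied criterion.** No section links not stopping with confirmation. The termination rule concerns grade 3 (or higher) events, whereas the endpoint is any complication, and the rule itself varies. It says when to stop, not when safety is shown.

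**Ten patients are not the only safety information.** Sections 5.4, 10.1 and 10.3 cite earlier rib work without identified or major adverse events. Pain, bleeding and infection are assessed (section 11.2.2), complications are reviewed every three months (section 13.1.1), and a yearly safety report is planned (section 12.4). The decision also needs feasibility. All this is fair, but none of it supplies a threshold, and section 10.1 itself calls the rib literature scarce.

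**The survey rates are not a benchmark for this endpoint.** Section 10.3 takes them from surveys of bone marrow biopsy, not from Clavien-Dindo-graded complications after thoracic surgery. I therefore draw no conclusion from comparing them with the pilot's result.

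**Conclusion.** The concern holds in this form: the large-scale study is conditional on a result that is undefined, while the protocol rules out any statement of uncertainty around it. With 0 complications in 10, rates up to 30.8% remain compatible at two-sided 95% confidence (25.9% one-sided). The pilot can show no more than the absence of a frequent problem. For feasibility, even 10 of 10 leaves a lower limit of 69.2%.

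These figures assume a 95% level, independent patients and all ten patients aspirated; the limit rises if fewer are. Severity: should be fixed. The conduct of the trial and the data collected are unaffected, but what the trial can be said to conclude changes.

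**What to change.** 1. In sections 13.4 and 13.1.1, and in the synopsis, replace the statements that there is no analysis with descriptive reporting of three proportions, each with an exact (Clopper-Pearson) two-sided 95% confidence interval: aspirated patients with any complication; aspirated patients with a grade 3 or higher complication; patients reaching 2×10^6 Lin- CD34+ HSPCs. No hypothesis test is needed.
2. State the actual denominators, both included and aspirated.
3. In sections 5.4 and 7.1, replace confirmed with wording that gives the observed count and its upper confidence limit. For example, 0/10 excludes only rates above about 31% at two-sided 95% confidence. Calculate the limit from the number actually aspirated.
4. Have the sponsor state beforehand what safety and feasibility results support the larger study.
5. Before the safety proportions are defined, reconcile the relatedness and termination wording. Section 7.2.4 counts patients with grade 3 events directly related to the aspiration. Section 11.1.7 counts patients with grade 3 or higher events and is silent on relatedness. Sections 12.1.4 and 12.2.2 count events. Section 12.1.2 speaks of related events, and section 12.2.1 of events that might be related. I propose no rule here; the sections must agree.

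The cost is one paragraph, two wording changes and a sponsor decision on the go criterion, with no extra patients or data. The downside is a less favourable safety statement.

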# 14 Ethical Considerations

## 14.1 Ethical conduct of the study

### 14.1.1 *Declaration of Helsinki*

The Investigator shall be responsible for ensuring that the clinical study is performed in accordance with the protocol, the ethical principles that have their origin in the Declaration of Helsinki (as amended by the 59th WMA General Assembly, Seoul, October 2008, to be found at [www.wma.net](http://www.wma.net)) as well as with the ICH Note for GCP (ICH, Topic E6, 1995) and applicable regulatory requirements. These documents state that the informed consent of subjects is an essential precondition for participation in the clinical study.

### 14.1.2 *Ethics Committee*

Prior to commencement of the study, the study protocol will be submitted together with its associated documents (informed consent, IB, insurance policy and insurance conditions, and all written information regarding this study to be provided to the subject or the subject's legal guardian) to the relevant IRB/EC for their favorable opinion/approval. The favorable opinion/approval of the IRB/EC will be filed in the Investigator Site File and a copy in the Study Master File by the Sponsor.

The study will only commence following provision of a written favorable opinion/approval. The date of the meeting, constitution of the committee, and voting members present at the meeting will be documented. Written evidence that clearly identifies the study, protocol version, and consent documents reviewed is required. Where possible, copies of the minutes of this meeting will be obtained.

## 14.2 Informed Consent

Each subject will sign an informed consent for participation in the clinical part of this study.

The written informed consent of the subject must be obtained before any study related activities are carried out. It must be signed and personally dated by the subject and by the Investigator/person designated by the Investigator to conduct the informed consent discussion.

The subject will be given sufficient time to read the information and the opportunity to ask questions and to request additional information and clarification about the study. The subject information sheet will be revised whenever important new information becomes available that may be relevant to the consent of subjects. Subjects with legal incapacity or limited legal capacity should be excluded from participation in the clinical study.

When informed consent is obtained, this will be documented in the CRF by the Investigator. The signed and dated declaration of informed consent will remain at the Investigator's site and must be safely archived by the Investigator so that the forms can be retrieved at any time for monitoring, auditing and inspection purposes. A copy of the signed and dated information and consent forms should be provided to the subject prior to participation.

## 14.3 Patient and Study Data Protection

A unique subject number will be assigned to a subject at inclusion, immediately after informed consent has been obtained. This number serves as the subject's identifier in the trial as well as in the clinical trial database. The subject's data collected in the trial will be stored under this number. Only the Investigator will be able to link the subject's trial data to the subject via an identification list kept at the site.

The subject's original medical data reviewed at the site during source data verification by the monitor, audits, and authority inspections, will be kept strictly confidential.

Data protection and privacy regulations will be observed in capturing, forwarding, processing, and storing subject data. Subjects will be informed accordingly and will be requested to give their consent on data handling procedures in accordance with national regulations.

#### 14.4 Subject Identification

All patients undergoing thoracic surgery for lung cancer will be screened by the principal investigator for inclusion in this trial.

### **15 Finance and Insurance**

For all subjects enrolled in the study, appropriate insurance coverage is provided in line with legal requirements and GCP guidance. Details can be asked for at the investigational site (certificates and conditions in the Investigator Site File). Insurance coverage shall be provided by a Global Insurance Provider. Since no additional visits are mandatory for this trial, no financial compensation is provided for the patients taking part in the trial.

### **16 Reporting and Dissemination**

Valuable data will be disseminated via national (e.g. ORC, BACR, *etc.*) and international conferences (e.g. CIMT, SITC, IASLC, ESMO, *etc.*). Moreover, the obtained results of the trial will be summarized for publication in a peer-reviewed journal with impact factor > 5. Finally, the co-investigator [name]. [name] will disseminate valuable results in layman's' terms as she gives seminars on a monthly basis to explain the concepts of cancer and immunotherapy to a broad audience.

### **17 Conflict of Interest Statement**

[name] MD has received financial compensations for talks on advanced hemodynamic management and proctoring sessions from Edwards Lifesciences.

[name] [name]: travel, accommodation, and expenses— Bristol-Myers Squibb, MSD, Pfizer

### **18 Tables and Figures**

Not applicable

